3.2 Secondary

Key Secondary

- The CGI-I score at Week 48
- Change from baseline in the MSA-QoL motor subscale at Week 48
- Change from baseline in the MSA-QoL non-motor subscale at Week 48
- Change from baseline in UMSARS Part I and II total score at Week 48

Other Secondary

- Change from baseline at Week 48 on the following instruments:
 - PGI-S,
 - CGI-S,
 - UMSARS Part III,
 - UMSARS Part IV.

[figure not shown]
4 STUDY PLAN

4.1 Study Design and Duration

BHV3241-301 is a Phase 3, multicenter, randomized, double-blind, 2-arm placebo-controlled parallel-group study designed to evaluate the efficacy and safety of BHV-3241 in a population of patients with MSA (MSA-C and MSA-P). The study is planned to consist of a Screening phase lasting a maximum of approximately 6 weeks and a randomized double-blind treatment phase of approximately 48 weeks, per Figure 2. It is anticipated that the Randomization phase will include a dose titration period of approximately 2 weeks followed by a full dose period of approximately 46 weeks. Approximately 325 subjects in total are planned to be randomized in a 1:1 ratio to receive either BHV-3241 600 mg BID, or matching placebo BID. It is anticipated that subjects will be assessed at clinic visits, per the Schedule of Assessments & Events (Table 1). In addition, subjects who are completing or have completed Week 48 of the double-blind treatment phase may be offered the opportunity to enroll in an Open-Label Extension phase, in which subjects will receive open-label treatment with BHV-3241 for approximately 48 weeks. (Table 2)

4.2 Study Schematic

Figure 2: Study Schematic

4.3 Schedule of Assessments

4.3.1 COVID-19 Public Health Emergency

In both the double-blind phase and OLE phase of the study, every effort should be made to conduct protocol-specified in-person study visits as planned and as close to the date of the scheduled visit as possible. However, due to the COVID-19 public health emergency, in order to minimize potential risks to the safety of study participants and study site personnel and to comply with government and local health care institution guidance and restrictions, study participants may be unable to attend study scheduled protocol required visits in person (e.g., shelter in place restrictions, study site policy that clinical research visits must be delayed). Under these circumstances, if a study participant is unable to attend an in person protocol-required evaluation at the study site at the scheduled time, the site Investigator should discuss the appropriate course of action and specific requirements for remote safety visits on a case by case basis with the Sponsor Medical Monitor (or designee), based on the specific study visit, the clinical status of the participant, consideration of their compliance to study medication, previous lab results and other risk factors.

Potential courses of action include expansion of the visit window, conduct of a remote [via phone or telemedicine video] visit, focusing on safety assessments during remote visits, including study drug compliance, concomitant medication review, adverse event monitoring, Sheehan Suicidality Tracking Scale, UMSARS Part I and Time to Event Measures, performing safety labs via local labs or in-home phlebotomy vendors, and shipping study medication to study participants, if needed. Vital signs, physical exams, and clinician-rated outcome measures (e.g., UMSARS Part II, CGI-I/S) will not be conducted remotely. ECGs may be conducted at a local health facility other than the study site, with subsequent submission to **CCI** (central ECG vendor). Screening, Baseline and Week 48 visits must be conducted in person and lab analyses should be conducted by **CCI** central lab.

For on-treatment study visits (not Screening, Baseline or Week 48), if the COVID-19 public health emergency prevents study subjects from being able to have blood and urine lab samples collected at the study site for shipment to **CCI** central lab for analysis, the samples may be collected at locations other than the study site (local lab, primary care practice, in-home phlebotomy service) and may be analyzed by a local lab. The study site will collect any local lab results for review and entry into the eDC eCRF. The safety lab samples collected and analyzed in these cases of remote assessments will be limited to safety labs specified by the Sponsor (see Section 6.2.2.4). Pharmacokinetic and **CCI** will not be collected.

4.3.1.1 *Criteria for Temporary Interruption of Investigational Product (IP)*

The visit windows for collection of BHV3241-301 protocol-required safety labs during the COVID-19 emergency, and the criteria for temporary interruption of IP due to inability to monitor patient safety via lab analyses are as follows:

- Week 4 or Week 4-Extension safety labs-need to be conducted within a 10 day window of Week 4 or Week 4-Extension. If not, need to temporarily interrupt IP until labs are conducted.
- Week 12 or Week 12-Extension safety labs-need to be conducted within a 8-week window of Week 12-Extension (assuming no clinically significant lab abnormalities at Week 8 or Week 8-Extension). For subjects who did not have Week 8 or Week 8 -Extension labs conducted, but who had Week 4 or Week 4-Extension labs conducted with no clinically significant lab abnormalities, then Week 12 or Week 12-Extension labs need to be conducted within a 4 week window of Week 12 or Week 12-Extension. If not, need to temporarily interrupt IP until labs are conducted.
- Week 24 or Week 24-Extension safety labs-need to be conducted within a 12-week window of Week 24 or Week 24-Extension (assuming no clinically significant lab abnormalities at Week 12 or Week 12-Extension). If not, need to temporarily interrupt IP until labs are conducted.

4.3.1.2 *Week 18 Assessment*

If a subject has not been assessed at an in person visit at Week 12 or Week 12-Extension, checking in with the subject remotely (by phone or video) between Week 12 or Week 12-Extension and Week 24 or Week 24-Extension (at approximately the Week 18 or Week 18-Extension timepoint) and obtaining safety labs is strongly encouraged. These labs may be conducted using the **CC** central lab Unscheduled Visit lab kit or they may be collected at a location other than at the study site (e.g., at a local lab or in the study participant's home via visiting phlebotomy service) and may be analyzed by a local lab.

4.3.1.3 *Shipment of Study Medication to Study Participants*

In these cases of remote assessments, when an in-person study visit is not possible due to the COVID-19 public health emergency, overnight shipment of study medication from the site to the study participant via certified and trackable courier under ambient conditions (following Remote Visit Workaround Guidelines provided to sites), is permissible, if acceptable to the study site's institution. Confirmation that the study drug shipment was received by the study participant should be retained as documentation, e.g., tracking confirmation printout from the courier, written documentation of contact with the subject (by phone, email, text), subject signature on packing list, etc.

4.3.1.4 *Remote Monitoring/Source Data Verification*

The on-site review and verification of study source documents by the Sponsor and its representatives may be affected by COVID-19 public health emergency restrictions limiting access to the study site. If it is specifically allowed according to health authority, IRB/EC and data protection agency regulations, remote source data verification may be conducted through Remote Monitoring, with study documents accessed electronically without breaking study participant confidentiality, according to **CCI** standard operating procedure.

Table 1: Schedule of Assessments and Events - Randomized Double-blind Phase

Visit	Screening Maximum of 42 days (-42 to -1)	Baseline (Pre-dose)	2*	3	3-1	4	5	6	7 ⁹	Week 48 Phone Call (if applicable) ¹⁰
Day (Visit procedures conducted within a +/- 3 day window, unless otherwise specified)		1	14	29	57	85	169	253	337 (+/- 7 days)	
Week		0	2	4	8	12	24	36	48 (Early D/C) ⁹	
Eligibility Assessments										
Informed Consent (subject and caregiver)	X									
Inclusion/Exclusion Criteria	X	X								
Medical History	X									
Demographic Data	X									
Concomitant Medication review	X	X	X	X	X	X	X	X	X	X
Safety Assessments										
Physical Examination*	X	X	X	X	X	X	X	X	X	
Physical Measurements ¹	X	X							X	
Vital Signs ²	X	X	X	X	X	X	X	X	X	
ECG (12-lead)	X	X	X	X	X	X	X	X	X	
Laboratory Tests	X	X	X	X	X	X	X	X	X	
Pregnancy Test ³	X	X		X		X	X	X	X	
Sheehan Suicidality Tracking Scale	X	X	X	X	X	X	X	X	X	
Adverse Event Reporting										
Monitor for Nonserious AEs		X	X	X	X	X	X	X	X	X
Monitor for SAEs	X	X	X	X	X	X	X	X	X	X

Visit	Screening	Baseline (Pre-dose)	2 ^a	3	3-1	4	5	6	7 ⁹	Week 48 Phone Call (if applicable) ¹⁰
Day (Visit procedures conducted within a +/- 3 day window, unless otherwise specified)	Maximum of 42 days (-42 to -1)	1	14	29	57	85	169	253	337 (+/- 7 days)	
Week		0	2	4	8	12	24	36	48 (Early D/C) ⁹	
Efficacy Assessments										
Unified MSA Rating Scale Parts I-IV*	X	X		X		X	X	X	X	
Clinical Global Impression of Severity (CGI-S)		X		X		X	X	X	X	
Clinical Global Impression of Improvement (CGI-I)				X		X	X	X	X	
Patient Global Impression of Severity (PGI-S)		X		X		X	X	X	X	
MSA Quality of Life		X					X		X	
CGI										
Time-to-event measures of disease progression		X		X		X	X	X	X	X ¹⁰
Other Assessments										
CGI										
Lumbar Puncture ⁵		X							X	
Pharmacokinetic Assessments										
Blood PK Sampling ⁶		X		X		X	X	X	X	
CGI										

Visit	Screening Maximum of 42 days (-42 to -1)	Baseline (Pre-dose)	2 ^a	3	3-1	4	5	6	7 ⁹	Week 48 Phone Call (if applicable) ¹⁰
Day (Visit procedures conducted within a +/- 3 day window, unless otherwise specified)		1	14	29	57	85	169	253	337 (+/- 7 days)	
Week		0	2	4	8	12	24	36	48 (Early D/C) ⁹	

CCI

Clinical Drug Supplies									
Randomize		X							
Dispense Study Drug		X		X		X		X	
Study Drug Compliance Assessment ⁸		X		X ^a		X		X	

Under regular circumstances, visits are to be completed in-person, unless otherwise specified. Some visits can be conducted remotely, as needed, due to COVID-19 restrictions. See Protocol Section 4.3.1, COVID-19 Public Health Emergency, for further details and requirements regarding conduct of remote visits due to COVID-19.

^a The Week 2 assessment should generally be conducted at the study site. Per Investigator judgement, additional evaluations/procedures may be conducted at this timepoint as appropriate.

^{*} Including neurologic exam as a component of general physical exam and UMSARS

¹ Height at Screening and Week 48; weight at Screening, Baseline, and Week 48.

² Subjects should be seated and resting for approximately 5 minutes prior to vital sign measurements - temperature, blood pressure, and heart rate. Tilt table may be used, if available.

³ Serum pregnancy test will be conducted in WOCBP (see section 5.5) at all scheduled visits. Urine pregnancy test will be performed on WOCBP (in addition to serum) at Baseline (within 24 hours prior to first dose).

CCI

CCI

⁶ One PK sample should be collected pre-dose and one PK sample should be collected post-dose. The time of the last BHV-3241/placebo dose prior to the sample collection and time of the PK sample collection and time of most recent meal should be reported on the CRF. At Weeks 4, 12, 24, 36 and 48, the morning dose of study drug should be held and administered in the clinic/office during the study visit, so that one pre-dose (trough) and one post-dose PK sample can be collected. The post-dose sample should be collected within a time window of approximately 2 to 4 hours. Collection of PK samples is not required at the Early Discontinuation visit.

CCI

⁸ Subjects should take the first dose of investigational product (IP) while in the office/clinic on the day of the Baseline visit and stay at the clinic for ~4 hours for observation. From start to end of Week 1, subjects will ingest either 300 mg QD of BHV-3241 or matching placebo QD. From start to end of Week 2, subjects will ingest either 300 mg BID of BHV-3241 or matching placebo BID. Starting with Week 3 and for the remainder of the double-blind portion of the study, subjects will ingest either 600 mg BID of BHV-3241 or matching placebo BID.

⁹ The Week 48 assessments/procedures should be conducted as an in person visit at the study site. Every effort should be made to conduct the Week 48 visit and maintain a +/- 7 day window. However, due to the COVID-19 public health emergency, if absolutely necessary, in order to minimize potential risks to study participant safety and to comply with governmental and local institutional guidance (e.g., study site has a policy that an in person clinical research visit must be delayed), the Week 48 visit window may be expanded up to an additional 12 weeks (maximum treatment duration of 60 weeks). However, every attempt should be made to conduct the visit as close as possible to the date that the visit is due. Under these circumstances, the Investigator should discuss the specific circumstances of these cases with the sponsor medical monitor (or designee), who must approve the request to extend the treatment duration, prior to any modification of the visit window. If the Week 48 visit window is modified, participants should have safety assessments evaluated remotely (e.g., via phone) and safety labs conducted (at a local lab) at the time of the scheduled Week 48 visit.

Subjects who discontinue from study medication prior to Week 48 will have an Early Discontinuation visit. Depending on the reason for the early discontinuation (e.g., declining patient status), some procedures, for example, PK samples, PD samples, lumbar puncture, may not be conducted at this visit. Conduct of all procedures, if possible, is encouraged.

¹⁰ For subjects who discontinue study medication early (prior to Week 48), the site should contact the subject by phone call at approximately Week 48 to collect information on clinical status (including Time to Event measures of disease progression, and if applicable, AEs, SAEs).

Table 2: Schedule of Assessments and Events - Open-Label Extension Phase

Visit	Baseline Ext ¹ (Pre-dose)	Abbreviated Drug Dispensation Visit ²	2 Ext (phone)	3 Ext ⁷ (can be remote)	4 Ext ⁷ (can be remote)	5 Ext	6 Ext	7 Ext	8 Ext ⁸
Day (Visit procedures conducted within a +/- 7 day window, unless otherwise specified)	1		14	29	57	85	169	253	337
Week	0		2 Ext	4 Ext	8 Ext	12 Ext	24 Ext	36 Ext	48 Ext/Early Discontinuation ⁸
Eligibility Assessments									
Informed Consent (subject)	X	X							
Medical History	X								
Concomitant Medication review	X	X				X	X	X	X
Safety Assessments									
Physical Examination ³	X					X	X	X	X
Physical Measurements ⁴	X								X
Vital Signs ⁵	X	X				X	X	X	X
ECG (12-lead)	X			X if visit is conducted in person	X if visit is conducted in person	X	X	X	X
Laboratory Tests	X			X	X	X	X	X	X
Pregnancy Test ⁶	X			X	X	X	X	X	X
Sheehan Suicidality Tracking Scale	X		X			X	X	X	X
Adverse Event Reporting									
Monitor for Nonserious AEs and SAEs	X	X	X	X	X	X	X	X	X

Visit	Baseline Ext ¹ (Pre-dose)	Abbreviated Drug Dispensation Visit ²	2 Ext (phone)	3 Ext ⁷ (can be remote)	4 Ext ⁷ (can be remote)	5 Ext	6 Ext	7 Ext	8 Ext ⁸
Day (Visit procedures conducted within a +/- 7 day window, unless otherwise specified)	1		14	29	57	85	169	253	337
Week	0		2 Ext	4 Ext	8 Ext	12 Ext	24 Ext	36 Ext	48 Ext /Early Discontinuation ⁸
Efficacy Assessments									
Unified MSA Rating Scale Parts I-IV ³ (if visit is conducted remotely [by phone], only conduct Part I)	X					X	X	X	X
MSA Quality of Life	X					X	X	X	X
Time-to-event measures of disease progression	X					X	X	X	X
Dispense Study Drug	X	X				X	X	X	X
Study Drug Compliance Assessment	X		X			X	X	X	X
Under regular circumstances, visits are to be completed in-person, unless otherwise specified. Some visits can be conducted remotely, as needed, due to COVID-19 restrictions. See Protocol Section 4.3.1, COVID-19 Public Health Emergency, for further details and requirements regarding conduct of remote visits due to COVID-19.									
¹ Baseline visit for the OLE Phase is only required if there is an extended break (≥4 weeks) in dosing between the double-blind and OLE Phases. Otherwise, the double-blind Week 48 visit will take the place of the Baseline-Extension visit. Subjects should take the first dose of IP while in the office/clinic on the day of the Baseline-Extension visit and stay at the clinic for ~4 hours for observation. From start to end of Week 1-Extension, subjects will ingest 300 mg QD of BHV-3241. From start to end of Week 2-Extension, subjects will ingest 300 mg BID of BHV-3241. Starting with Week 3-Extension and for the remainder of the OLE, subjects will ingest 600 mg BID of BHV-3241.									
² Abbreviated visit only needed for patients who completed dosing in the double-blind phase <4 weeks prior to entering the OLE Phase. The double-blind Week 48 Visit serves as the Baseline-Extension visit. This visit is primarily to dispense study drug. Subjects should take the first dose of IP while in the office/clinic on the day of the Baseline-Extension visit and stay at the clinic for ~4 hours for observation. From start to end of Week 1, subjects will ingest 300 mg QD of BHV-3241. From start to end of Week 2, subjects will ingest 300 mg BID of BHV-3241. Starting with Week 3 and for the remainder of the OLE, subjects will ingest 600 mg BID of BHV-3241.									
³ Including neurologic exam as a component of general physical exam and UMSARS.									
⁴ Height and weight.									
⁵ Subjects should be seated and resting for approximately 5 minutes prior to vital sign measurements - temperature, blood pressure, and heart rate. Tilt table may be used, if available.									

⁶ Serum pregnancy test will be conducted in WOCBP (see section 5.5) at all scheduled visits. Urine pregnancy test will be performed on WOCBP (in addition to serum) at Baseline-Extension (within 24 hours prior to first dose of open-label BHV-3241).

⁷ Week 4-Extension and Week 8-Extension are primarily to collect lab tests and, if conducted in the clinic/study site, to conduct an ECG. If the patient attends the visit at the clinic/study site, an assessment of adverse events, conduct of an ECG and collection of samples for lab analyses will be completed. If a participant prefers to not attend the visit at the clinic/study site, the lab samples can be collected/conducted at a local laboratory/location and a telephone call to confirm these were collected, as well to assess any adverse events, will take place.

⁸ Subjects who discontinue from study medication prior to Week 48-Extension will have an Early Discontinuation visit

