If there are clinically significant issues with tolerability that are not able to be treated adequately with thyroxine replacement therapy, the Investigator may consider modifications to the dosage regimen. Consultation with the Medical Monitor is required. Modifications may include reducing the dose of BHV-3241/matching placebo to 300 mg BID or taking a dose holiday. Any such modifications to the dosage regimen should be noted in the CRF.

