6.2.6.1 Study Therapy

Double-Blind Phase

For the double-blind phase, the extent of subject exposure (i.e., treatment duration) will be quantified as the number of days on study medication and measured from the time the subject received the first dose of study medication until the time the subject received the last dose of study medication. Treatment duration includes missed dose days; i.e., last dose date of double-blind randomized study medication – first dose date of double-blind randomized study medication + 1.

The extent of subject exposure (i.e., total days on study medication) will also be calculated for each subject by counting days where the number of tablets taken was > 0 (i.e., treatment duration – number of days a subject missed all doses of double-blind randomized study medication). If a subject took at least one dose of study medication on a study day, then the subject will be counted as having received study medication on that day.

Additionally, percent (%) compliance will be calculated as (total days on double-blind randomized study medication) / (treatment duration of double-blind randomized study medication) \times 100.

The number and percentage of subjects who had dose titrations during the double-blind phase will also be summarized by time point and dose.

Open-Label Extension Phase

For the OLE Phase, the extent of subject exposure (i.e., treatment duration) will be quantified as the number of days on study medication and measured from the time the subject received the first dose of study medication in the OLE Phase until the time the subject received the last dose, either at the end of the study or withdrawal from the OLE Phase. Treatment duration includes missed dose days, i.e., last dose date of OLE study medication – first dose date of OLE study medication + 1.

The extent of subject exposure (i.e., total days on study medication) during the OLE Phase will also be calculated for each subject by counting days where the number of tablets taken was > 0 (i.e., treatment duration – number of days a subject missed all doses of OLE study medication). If a subject took at least one dose of study medication on a study day, then the subject will be counted as having received study medication on that day.

Additionally, percent (%) compliance will be calculated as (total days on open-label Verdiperstat study medication) / (treatment duration of open-label Verdiperstat study medication) × 100.

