6.3.2.2 Supplementary Analyses

The estimand for the first supplementary analysis will pursue a while on-treatment strategy. This will use the mITT population. The endpoint will be the change from baseline in the modified UMSARS score at the last measured time point. For subjects that stay on study, this will be the Week 48 visit. For subjects that discontinue early, the last on-treatment visit will be used as the endpoint. The population summary will be the difference between placebo and Verdiperstat treated subjects at their last visit. The summary will be computed using an Analysis of Covariance (ANCOVA), estimated by Restricted Maximum Likelihood (REML) that will include fixed effect factors for treatment group and randomization strata. Baseline modified UMSARS score will be used as a covariate.

The estimand for the second supplementary analysis will pursue a hypothetical strategy that estimates the effect of treatment in compliant subjects. The endpoint and population summary will be the same as used for the primary estimand. However, the population and handling of intercurrent events will be handled differently. The population will consist of subjects that are at least 80% compliant with the drug regimen and complete the Week 48 visit. In terms of intercurrent events, subjects that discontinue treatment, or are lost to follow-up, before Week 48 are not included in the analysis.

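### SAP 6.2.6.1 ends the compliance denominator at the last dose, so a drug interruption still open at Week 48 can score 100% and pass the 80% rule of Supplementary Analysis 2

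*Protocol*

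**What the plan says.** **Compliance formula (SAP 6.2.6.1).** Percent compliance in the double-blind phase is total days on study medication divided by treatment duration, times 100. The numerator is obtained by "counting days where the number of tablets taken was > 0". The denominator is "last dose date of double-blind randomized study medication – first dose date of double-blind randomized study medication + 1". The SAP adds that "Treatment duration includes missed dose days", but with this definition only missed days before the last dose can count.

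**Where the score is used (SAP 6.3.2.2).** For the second supplementary analysis of the primary endpoint, "The population will consist of subjects that are at least 80% compliant with the drug regimen and complete the Week 48 visit". Subjects who stop treatment or are lost before Week 48 are left out. The section gives no compliance formula of its own, so that of 6.2.6.1 is the only one available.

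**How gaps in dosing arise.** Protocol 4.3.1.1 sets lab deadlines under the COVID-19 provisions. The latest reads "Week 24 or Week 24-Extension safety labs-need to be conducted within a 12-week window of Week 24 or Week 24-Extension", followed by "If not, need to temporarily interrupt IP until labs are conducted". Separately, Protocol 8.1.8 lists "or taking a dose holiday" among the possible dose modifications for thyroid-related tolerability problems. Neither section sets a maximum length or says when an unresumed interruption becomes a discontinuation. Protocol 6.4 does not list one among its reasons for mandatory discontinuation.

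**The concern.** The second supplementary analysis is meant to estimate the treatment effect in subjects who took the drug. A threshold on compliance does that only if similar dosing histories get similar scores. Here the score depends on whether the off-drug period is closed by a later dose. A closed gap counts in full as missed days, while the same gap still open at Week 48 drops out of the denominator. The rule could then keep a subject with no drug for the 12 weeks before the endpoint and remove one who was off drug for less time. What is at stake is who belongs to one supplementary analysis set, and how far the compliance summary can be read as a measure of drug taken up to the endpoint.

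**Working it through.** The documents state no compliance percentage, so there is no plan figure to reproduce. The check applies the SAP formula directly.

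**Inputs from the documents**
- Week 24 is Day 169 and Week 48 is Day 337 (SAP 7.2, Table 5).
- The Week 24 labs have a 12-week limit (Protocol 4.3.1.1): 169 + 84 = Day 253.
- Compliance = days with drug / (last dose day − first dose day + 1).

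**Assumptions**
- The first dose is on Day 1 and no other days are missed.
- Drug is taken through Day 253 and stopped from Day 254 because the labs are still outstanding.
- The Week 48 visit is on Day 337.
- The subject is not classed as having discontinued treatment.

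**Results**

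| Double-blind dosing after Day 253 | Days with drug | Score, denominator to last dose | Score, denominator to Day 337 |
|---|---|---|---|
| None | 253 | 253/253 = 100% | 253/337 = 75.1% |
| One day, Day 317 | 254 | 254/317 = 80.1% | 254/337 = 75.4% |
| One day, Day 336 | 254 | 254/336 = 75.6% | 254/337 = 75.4% |
| One day, at the Week 48 visit | 254 | 254/337 = 75.4% | 254/337 = 75.4% |

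The four subjects differ by at most one dosed day. Under the current formula the first two pass 80% and the last two fail. With the denominator ended at the visit, all four fall below 80%.

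**Comparison with a closed gap.** A subject interrupted for 68 days in mid-course and then dosed through Day 336 scores (336 − 68)/336 = 268/336 = 79.8% and is removed. The first subject in the table is kept with 337 − 253 = 84 days between last dose and endpoint.

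**Sensitivity of the worked case**
- If the 12 weeks run from the late edge of the Week 24 visit window (Day 172), the last dose is Day 256. One more dose on Day 336 gives 257/336 = 76.5%.
- Under the earlier triggers an unresumed subject also scores 100% now. To Day 337 the scores would be 141/337 = 41.8% (Week 12 plus 8 weeks), 113/337 = 33.5% (Week 12 plus 4 weeks) and 39/337 = 11.6% (Week 4 plus 10 days).
- If the Week 48 visit is delayed by the permitted 12 weeks to Day 421, the unresumed subject still scores 253/253 = 100%, against 253/421 = 60.1% to the visit date.

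**Why the denominator alone is not enough.** With the denominator at Day 337, an otherwise fully adherent subject last dosed on Day 277 scores 277/337 = 82.2% and passes, although the assessment is 60 days after the last dose. SAP 7.1 ends the on-treatment period for efficacy 7 days after the last dose, and that limit would catch this subject.

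**The case against.** **A dose is scheduled at Week 48.** Protocol 4.3.3 and 7.2.2 have the morning dose given at the Week 48 visit for PK sampling. That visit is in person with labs, so the condition for the interruption may be met there. If the dose is given, the 100% becomes 75.4% and the subject is correctly removed. This is the strongest point, and it narrows the problem. It does not close it: Protocol 7.2.1 excepts Week 48 from the visits at which drug is assigned and dispensed, and nothing says that an interrupted subject is dosed there. A single PK-visit dose would also then decide membership of the set.

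**Discontinuers are already excluded.** A subject never dosed again after Day 253 could reasonably be classed as having discontinued. A reader might equally infer that a temporary interruption is never a discontinuation. The documents support neither reading, because they do not define the boundary.

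**SAP 7.1 may already mark the value as off treatment.** The 7-day limit would do so, but SAP 6.3.2.2 does not invoke it for this analysis.

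**The case is contrived.** Labs must stay undone past Week 24 and through Week 36, despite the local-lab and in-home options, until Week 48. That stands: such cases are likely to be uncommon. The Week 4 and Week 12 triggers and dose holidays are other routes.

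**Stronger readings that do not hold**
- A reader might infer arm imbalance, because earlier studies showed TSH rising relative to placebo. The protocol also says that most values stayed in range and abnormalities were mild (1.4). It makes a dose holiday one option when thyroxine is not adequate (8.1.8). No rate by arm is given, and the lab-deadline route has no treatment-related mechanism.
- A reader might infer that the reported compliance percentages are wrong. They follow an openly stated first-to-last-dose convention, and days on drug are reported as well.
- A reader might take the lab-interruption rule to be at fault. The problem lies in the SAP denominator, not in that safety rule.

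**Conclusion.** The point holds as a minor one. SAP 6.2.6.1 does not count time off drug after the last dose, and SAP 6.3.2.2 relies on that score without a rule for interruptions still open at Week 48.

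The size is 100% against 75.6% for two subjects who differ by one dosed day, on opposite sides of the 80% line. It rests on three conditions: the interruption or dose holiday is still open at Week 48, no dose is given at that visit, and the subject is not classed as having discontinued. The exact figures also assume a first dose on Day 1, no other missed days and the Week 24 trigger.

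How many subjects would meet these conditions cannot be known from the documents. The effect is confined to the second supplementary analysis and to how the compliance summaries are read. The primary MMRM, the Hochberg procedure and the key secondary tests do not use this score.

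**What to change.** - **SAP 6.3.2.2, denominator.** For the 80% criterion, end the compliance denominator at the actual Week 48 visit date. Every subject in this set completes Week 48 and treatment discontinuers are already excluded, so no separate end date is needed for them.
- **SAP 6.3.2.2, recency.** Require the Week 48 assessment to fall no later than 7 days after the last double-blind dose, by reference to SAP 7.1. An unresumed subject is then excluded whether or not the interruption is called a discontinuation.
- **SAP 6.2.6.1.** The first-to-last-dose percentage can stay as a descriptive summary. Add a line tabulating interruption days by arm, including days after the last dose up to Week 48.

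This is a few words of SAP text using dosing and visit dates that the SAP already relies on. The downside is a slightly smaller supplementary set. No change to the clinical interruption rule is proposed.
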